#### Image Segmentation and Tortuosity Quantification

In order to derive quantitative vessel tortuosity metrics for the acoustic angiography images, we will perform an image processing workflow. The de-identified DICOM images will be converted to a 3-D volume and linearly up-sampled using MATLAB to create isotropic 50 x 50 x 50 micron voxels. Then, the lesion will be manually segmented to identify a region of interest (ROI) for vessel analysis. Using a series of algorithms [59, 60], each vessel in the ROI will be segmented and a series of tortuosity metrics will be calculated. The vessels are segmented using semi-automated multi-scale ridge traversal and stored as a series of center-line point coordinates (x,y,z) forming a spline. The radius of the vessel is estimated at each point and saved as a fourth parameter. [14, 61] Each

tortuosity metric will be used individually to contrast benign and malignant lesions using a two-sided t-test, incorporating a Bonferroni correction to account for multiple hypothesis testing.

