### 10.1 Sample Size and Accrual

Per the revision in increased Perflutren dose, we have updated our sample size statistics as follows.

For power calculation, the null hypothesis is that the specificity of acoustic angiography system is the same as the standard of care (b-mode ultrasound), which is assumed to be 70%. (We will determine the specificity of b-mode ultrasound during the trial to confirm that the 70% represents the specificity in the hands of UNC radiologists) Under the alternative, we expect that the specificity of the new device is at least 90%. The specificities are measured relative to pathological diagnosis as the reference standard. With 60 lesions and 5 readers, where we anticipate that roughly half will be malignant, assuming the correlation from the same patient to be 0.5 and the readers to read different patients independently, the power to see specificity at least larger than 90% is 98% at the significance level 0.05 using one-side test. With 50 lesions (half are benign), the power to see specificity of 90% is >96%; with 25 lesions (about 13 are benign), this power becomes 72%. The power to reject the null hypothesis is 98%. Although we will study both sensitivity and specificity, our power calculation is based on specificity, which is the primary interest.

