### 10.2.2 Secondary Analyses

#### Radiologist Preference

The secondary analysis will be to estimate the receiver operating characteristic (sensitivity and specificity) curve for the acoustic angiography system, with an additional aim of evaluating reader preference for specific breast lesion characteristics. Specifically, to compare the diagnostic performance, we will non-parametrically calculate the area under the ROC curve for each reader and each modality, where the ROC curve is derived using the different cut-off of the probability scores across 60 patients. We then fit a mixed effect model, where the outcomes are the estimated area under the ROC curves and the fixed effect is the dummy variable of the acoustic angiography system vs. conventional b-mode ultrasound. The readers will be treated as random effect. F-test from model fitting will be used to test whether the acoustic angiograph has a significant larger AUC than the conventional b-mode ultrasound (with significance level 0.05).

To assess the reader preference for modality for each characteristic including shape, margins and vascularity, we will fit a random effect model with only intercept and random terms for patients and readers while the outcomes are the confidence scores (-3 to +3) . By testing the intercept significantly larger than zero, we will conclude that the new modality provides more confidence for readers than the conventional one.

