#### Predicting Malignancy

In order to predict malignancy based on the quantitative vessel tortuosity metrics, the set of images will be randomly divided into two halves to form a training data set and a test data set. The malignant lesions and the benign lesions will be randomly assigned to the training or test group separately to ensure that both groups contain both types of images. Multivariate binary logistic regression will be used to predict malignancy based on the full set of tortuosity metrics for the training data set of 30 images. We will examine the model for multicollinearity using pairwise correlations and perform linear discriminant analysis to choose a smaller subset of metrics if over-fitting due to multicollinearity appears to be a problem. The model will then be used to predict the probability of malignancy of the test set of 30 images (via development of a model-based malignancy score). We will construct a receiver operator curve (ROC) by determining the sensitivity and specificity of the model when varying the threshold of probability of malignancy. We can then compare the performance of the quantitative tortuosity model to the reader study by comparing the area under the curve for both ROCs.

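### Free improvement to a secondary analysis: replace plain Bonferroni with Holm's step-down procedure for the tortuosity t-tests, on one value per metric per lesion

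*Combined protocol and SAP*

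**What the plan says.** The tortuosity analysis is in section 10.2.2, under Image Segmentation and Tortuosity Quantification. Within the lesion's region of interest, "each vessel in the ROI will be segmented and a series of tortuosity metrics will be calculated". Each "tortuosity metric will be used individually to contrast benign and malignant lesions using a two-sided t-test, incorporating a Bonferroni correction". The text does not list or count the metrics and states no significance level for these tests. The neighbouring comparison of areas under the curve is made "with significance level 0.05".

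Two other places give the scale and the unit. Section 10.1 plans "With 60 lesions and 5 readers, where we anticipate that roughly half will be malignant", so about 30 benign and 30 malignant lesions. Under Predicting Malignancy, the same metrics enter a logistic regression to "predict malignancy based on the full set of tortuosity metrics for the training data set of 30 images", with another 30 images as the test set. That means one record per image.

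**The concern.** Secondary objective 2.2.3 is to quantify tortuosity metrics and build a malignancy model from them. The t-tests say which metrics differ between benign and malignant lesions. Bonferroni holds every metric to the strictest threshold, the level divided by the number of metrics, even after other metrics have already been declared different. Holm relaxes the threshold step by step and keeps the same guarantee on familywise error.

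What is at stake is the list of metrics declared different. With several real differences, Bonferroni can leave some off the list that Holm would include. The primary comparison of sensitivity and specificity is unaffected, and so is the validity of any rejection that Bonferroni makes.

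**Working it through.** The plan gives no power, level or number of metrics for these tests, so there is no stated figure to reproduce.

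**Inputs**
- From section 10.1: 60 lesions, roughly half malignant, so 30 v 30.
- From section 10.2.2: a two-sided two-sample t-test per metric, with Bonferroni.
- Assumed: familywise level 0.05 (borrowed from the neighbouring test), k = 6 metrics, equal pairwise correlation 0.7, true shift 0.7 SD on the metrics that differ, and one value per metric per lesion.

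**Thresholds**
- Bonferroni: every p-value is compared with 0.05/6 = 0.0083.
- Holm: the ordered p-values are compared with 0.05/6, 0.05/5, 0.05/4, 0.05/3, 0.05/2 and 0.05/1, that is 0.0083, 0.0100, 0.0125, 0.0167, 0.0250 and 0.0500, stopping at the first failure.

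No Holm threshold is below 0.0083, and the first equals it. Two facts follow without simulation. Holm rejects every hypothesis that Bonferroni rejects. Both reject at least one hypothesis in exactly the same data sets, because each then needs the smallest p-value to be at or below 0.0083.

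**Bonferroni power for one metric**
- Non-centrality = 0.7 × √(30 × 30/60) = 0.7 × √15 = 2.71.
- The two-sided critical value at 0.0083 on 58 degrees of freedom is 2.73.
- Power ≈ Φ(2.71 − 2.73) = Φ(−0.02) ≈ 0.49, in line with the simulated 50%.

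**Share of true differences detected (simulation, inputs as above)**

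| Metrics that truly differ | Bonferroni | Holm |
|---|---|---|
| 6 of 6 | about 50% | about 60% |
| 3 of 6 | about 50% | about 53% |
| 1 of 6 | about 50% | unchanged |

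With all six metrics different, the chance of at least one detection is 78% under both methods. The Holm gain does not depend on correlation: with six uncorrelated metrics that all differ, the figures are 50% and 61%.

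**Is Bonferroni valid here?** Yes. With 5 metrics and no true difference, its simulated familywise error is 0.048 at correlation 0, 0.030 at 0.8 and 0.019 at 0.95, never above 0.05.

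**What a max-T threshold would add.** A single-step max-T threshold was compared with Bonferroni for 3 to 10 metrics and a 0.75 SD shift on all of them. The gain in power per metric is at most about 3 points at correlations up to 0.5, about 5 to 12 points at 0.8, and about 9 to 21 points at 0.95. With only one of six metrics different and a 0.7 SD shift, step-down max-T detects it in 57% against 50% at correlation 0.7, and in 51% against 49% at correlation 0.3. The documents give no correlation, so this gain cannot be promised.

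**The case against.** The best defence is that nothing here is an error. Bonferroni controls the familywise error at any correlation, the analysis is secondary, and conservatism is a legitimate choice. Most of that stands. The power gain also depends on a favourable case: it is clear when many metrics differ, small when half do, and nil when one does. Holm gets its extra rejections by spending error that Bonferroni leaves unused, although it stays within the same familywise limit. What remains is that Holm matches or beats Bonferroni on every data set under the same guarantee and the same absence of assumptions, so there is no statistical reason to keep the weaker procedure.

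A reader might infer something more serious: since each vessel is segmented before "a series of tortuosity metrics will be calculated", vessels could enter the t-tests as independent observations, which would inflate the false-positive rate. The text does not say this. The contrast is between benign and malignant lesions, and the same metrics go into data sets of 30 images. The rule for summarising vessels into a lesion value is unstated, and the cited segmentation and tortuosity sources, which may define it, are not available here. That is missing detail about the summary and does not show a vessel-level test.

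A reader might also infer that the plan suspects its metrics to be collinear and so undermines its own choice of Bonferroni. The text plans a check of the logistic model, "We will examine the model for multicollinearity using pairwise correlations", and a smaller set of metrics only "if over-fitting due to multicollinearity appears to be a problem". That is a conditional diagnostic for a different analysis and states no expectation.

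**Conclusion.** The point holds as a free improvement of low severity. The planned tests are valid, and Holm is at least as powerful at the same familywise level without any assumption on correlation. Under the assumed 30 v 30 lesions, 6 metrics, correlation 0.7 and shift 0.7 SD, the gain in true differences detected is about 10 percentage points if all metrics differ, about 3 if half do, and none if one does. The chance of detecting at least one difference does not rise. The ordering of the two methods is certain. The size of the gain is illustrative, because the number of metrics, their correlation and the effect size are not in the documents. The documents do not support reading this as a finding that Bonferroni is wrong.

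**What to change.** In section 10.2.2, under Image Segmentation and Tortuosity Quantification, replace the Bonferroni correction with Holm's step-down procedure at the same familywise level. Say that the tests use one value per metric per lesion, so that the unit already implied is explicit. Holm needs the level and the number of metrics, as Bonferroni does, so the same sentence should give both. A step-down max-T permutation test across metrics may be named instead if the team expects highly correlated metrics, but it is not needed.

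The cost is a sentence or two of SAP wording. Holm is a re-ranking of p-values that will be computed anyway. There are no new data, no change in sample size and no change in the error guarantee. The max-T option would also need a short permutation program.

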#### Predicting Malignancy

In order to predict malignancy based on the quantitative vessel tortuosity metrics, the set of images will be randomly divided into two halves to form a training data set and a test data set. The malignant lesions and the benign lesions will be randomly assigned to the training or test group separately to ensure that both groups contain both types of images. Multivariate binary logistic regression will be used to predict malignancy based on the full set of tortuosity metrics for the training data set of 30 images. We will examine the model for multicollinearity using pairwise correlations and perform linear discriminant analysis to choose a smaller subset of metrics if over-fitting due to multicollinearity appears to be a problem. The model will then be used to predict the probability of malignancy of the test set of 30 images (via development of a model-based malignancy score). We will construct a receiver operator curve (ROC) by determining the sensitivity and specificity of the model when varying the threshold of probability of malignancy. We can then compare the performance of the quantitative tortuosity model to the reader study by comparing the area under the curve for both ROCs.

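### The malignancy model is trained on one random half of the 60 lesions and tested on the other half: sound for that half-sample model, but inefficient and split-dependent, when cross-validation on all 60 would need no new data

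*Combined protocol and SAP*

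**What the plan says.** In Section 10.2.2, Predicting Malignancy, "the set of images will be randomly divided into two halves to form a training data set and a test data set". The split is stratified by pathology: "The malignant lesions and the benign lesions will be randomly assigned to the training or test group separately". Logistic regression is then used to "predict malignancy based on the full set of tortuosity metrics for the training data set of 30 images". Pairwise correlations are inspected, and the analysts may "perform linear discriminant analysis to choose a smaller subset of metrics if over-fitting due to multicollinearity appears to be a problem". For evaluation, "The model will then be used to predict the probability of malignancy of the test set of 30 images", a ROC curve is drawn, and the model is set against the readers by "comparing the area under the curve for both ROCs".

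Three other places matter:
- Section 10.2.2, Image Segmentation and Tortuosity Quantification: "a series of tortuosity metrics will be calculated", and each "tortuosity metric will be used individually to contrast benign and malignant lesions using a two-sided t-test". The number of metrics is not given in the text; the sources cited there may define it.
- Section 10.2.2, Radiologist Preference: the reader ROC curves are derived over 60 patients.
- Section 10.1: 60 lesions, about half of them malignant.

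The plan names no repeated splitting, cross-validation or seed, no expected AUC for the model, and no standard error or interval for the model AUC. The bootstrap in Section 10.2.1 covers reader sensitivity and specificity only.

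**The concern.** Objective 2.2.3 includes developing a malignancy model, and objective 2.2.4 compares it with the readers. Halving 60 lesions leaves about 15 malignant and 15 benign for fitting, and the same for testing. The model learns from half of the information, its AUC is measured on half, and a different random draw from the same women would give a different headline figure. The comparison in 2.2.4 then sets a 30-lesion model AUC beside a 60-patient reader AUC. The screen before fitting looks for multicollinearity; it would not notice over-fitting from too many uncorrelated metrics.

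At stake are the precision and reproducibility of one secondary result and the quality of the model carried forward. The primary analysis and the t-tests on individual metrics are untouched.

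**Working it through.** **1. What the plan's own figures cover.** 60/2 = 30 + 30 agrees with the text. The only stated basis for 60 lesions is the specificity power in Section 10.1. Effective n = 5 × 30/(1 + 4 × 0.5) = 50. Power = Φ[(0.20 − 1.645 × √(0.7 × 0.3/50))/√(0.9 × 0.1/50)] = Φ[(0.200 − 0.107)/0.0424] = 98.6%, against the stated 98%. No precision is stated for the model, so nothing there bears on this point.

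**2. Precision without simulation (Hanley-McNeil).** Var = [A(1−A) + (n₁−1)(Q₁−A²) + (n₀−1)(Q₂−A²)]/(n₁n₀), with Q₁ = A/(2−A) and Q₂ = 2A²/(1+A). At A = 0.80, Q₁ = 0.667 and Q₂ = 0.711.
- 15/15: (0.16 + 14 × 0.0267 + 14 × 0.0711)/225 = 0.00680; SE 0.082, 95% half-width 0.162.
- 30/30: (0.16 + 29 × 0.0267 + 29 × 0.0711)/900 = 0.00333; SE 0.058, half-width 0.113.

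The half-widths at 0.70 are 0.189 and 0.133, and at 0.90 they are 0.117 and 0.082. The 30/30 figure only approximates cross-validation, because the fold predictions are not fully independent.

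**3. Simulation inputs.** From the documents: 60 lesions, about 30/30, stratified halves. Assumed: 3, 5, 7 or 10 Gaussian metrics, independent in the base case; attainable AUC 0.80, with 0.70 and 0.90 as the range; 1200 data sets per cell. Ridge penalties are tuned by inner 5-fold deviance. The discriminant-analysis step is not simulated.

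**4. Bias of the split at AUC 0.80, unpenalised.** Mean test AUC is 0.769, 0.738, 0.716, 0.680. The true AUC of the half-sample model is 0.765, 0.741, 0.716, 0.679. Training AUC is 0.83, 0.86, 0.89, 0.93. Over-fitting shows in the training half and lowers the test AUC; it does not inflate it.

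**5. Variance, same penalty in both designs, AUC 0.80.**

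| Metrics | Split SD, unpenalised | CV SD, unpenalised | Ratio | Split SD, ridge | CV SD, ridge | Ratio |
|---|---|---|---|---|---|---|
| 3 | 0.094 | 0.066 | 2.1 | 0.090 | 0.069 | 1.7 |
| 5 | 0.101 | 0.069 | 2.2 | 0.093 | 0.074 | 1.6 |
| 7 | 0.105 | 0.069 | 2.3 | 0.102 | 0.075 | 1.9 |
| 10 | 0.117 | 0.078 | 2.3 | 0.104 | 0.083 | 1.6 |

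The ratio is (split SD/CV SD)², from unrounded SDs. At AUC 0.70 the ratios are 1.5–1.9 (unpenalised) and 1.4–1.6 (ridge); at 0.90 they are 2.3–3.6 and 2.0–2.2. With metric correlation 0.5 at AUC 0.80 they are 2.0–2.2 and 1.9–2.1.

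**6. Dependence on the draw.** At AUC 0.80, re-splitting the same 60 lesions gives SD 0.066, 0.074, 0.081, 0.090, with a 5th-to-95th percentile span of 0.20 to 0.27. A separate simulation (2, 4 or 8 metrics, correlation 0.3, attainable AUC 0.75–0.90) gave 0.044–0.083.

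**7. RMSE against the true AUC of the model each design reports.**
- Ridge in both, AUC 0.80 (400 data sets): split 0.083, 0.083, 0.093, 0.087; CV 0.070, 0.073, 0.079, 0.079. Reductions: 16, 12, 15 and 9%.
- Unpenalised in both, 2, 4 and 8 metrics: at AUC 0.75, 0.089, 0.096, 0.108 falls to 0.068, 0.076, 0.085 (24, 21, 21%); at 0.85, 0.065, 0.080, 0.083 falls to 0.049, 0.060, 0.066 (25, 25, 20%).
- AUC 0.70: 0.099–0.104 against 0.091–0.101. This compares an unpenalised split with ridge CV, and the gain is still small.

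**8. Where the weaker model comes from (true AUC; 400 data sets, attainable 0.80).**

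| Metrics | Half, unpenalised | Half, ridge | All 60, ridge | Gap due to penalty | Gap due to sample size |
|---|---|---|---|---|---|
| 3 | 0.769 | 0.774 | 0.786 | 0.005 | 0.012 |
| 5 | 0.739 | 0.753 | 0.774 | 0.014 | 0.021 |
| 7 | 0.711 | 0.735 | 0.762 | 0.024 | 0.027 |
| 10 | 0.680 | 0.720 | 0.749 | 0.040 | 0.029 |

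At 7 to 10 metrics about half of the gap or more (0.024/0.051 and 0.040/0.069) is the missing penalty, which could be added while keeping the split.

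**9. Interval for model minus reader AUC** (5 and 10 metrics, 500 data sets; assumed: five readers at AUC 0.80, between-reader correlation 0.5, reader-to-model 0.3).

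| Method | Bootstrap SE | Actual SD | Coverage of 95% interval |
|---|---|---|---|
| CV, refit bootstrap | 0.100, 0.110 | 0.075, 0.077 | 99.0%, 98.8% |
| CV, fixed out-of-fold scores | – | – | 88.2%, 89.6% |
| Split, bootstrap of 30 test lesions | 0.093, 0.103 | 0.106, 0.118 | 93.4%, 93.0% |

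**The case against.** A held-out half is a recognised design, the objective is secondary, and the plan attaches no test or decision to it. Cross-validation gives up the only untouched test set. The gain in RMSE is modest, and small at AUC 0.70. The reported interval would not shrink: the refit bootstrap is about 7% wider than the split-sample one (0.100/0.093, 0.110/0.103) and over-covers, while the split's own interval is closest to nominal. The base case assumes independent metrics, whereas the plan expects multicollinearity and may drop some.

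All of this stands, and it limits the point to a cheap improvement. It does not remove the dependence on one draw or the larger sampling variance, which persist with ridge in both designs and with correlated metrics.

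Some stronger readings are tempting but unsupported:
- A reader might infer that 30 images and many metrics inflate the reported AUC. The AUC comes from held-out images, so over-fitting lowers it.
- A reader might infer that the reader lesion set is unspecified. Section 10.2.2, Radiologist Preference, uses 60 patients; the issue is a mismatch of 60 with 30. Matching on the same 30 does not restore precision: the SD of the difference is 0.094–0.117 unmatched and 0.099–0.120 matched.
- A reader might blame the split for all of the lost accuracy. Step 8 shows that part is the missing penalty.

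**Conclusion.** The plan contains no error of validity here, provided metric selection uses the training half only. The order of the text implies this but does not say so, and the t-tests on individual metrics must not feed the selection. The design is inefficient. Like for like, cross-validation on all 60 lowers the variance of the AUC estimate by a factor of about 1.4 to 2.2 with ridge and 1.5 to 3.6 unpenalised. It lowers RMSE by roughly 10 to 25% at an attainable AUC of 0.80, and less at 0.70. A single split carries a re-split SD of about 0.04 to 0.09.

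These sizes rest on assumed metric counts (2 to 10) and attainable AUCs (0.70 to 0.90), because the documents give neither. The direction was the same in every scenario. A reader might infer that the comparison in 2.2.4 is invalid or that the fix yields a tighter reported interval; neither follows. The change is worth making as a low-cost improvement to model development in 2.2.3 and to 2.2.4.

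**What to change.** - List the tortuosity metrics and their number.
- Replace the single split by repeated stratified 10-fold cross-validation over all 60 lesions. Do scaling, metric selection and any penalty tuning inside the folds. Keep all lesions of one patient in one fold, since Section 3.1.2 allows more than one. A penalised logistic model is advisable.
- Fit the final model on all 60 lesions.
- Compare its cross-validated AUC with the reader-averaged acoustic angiography AUC on the same 60 lesions, using a patient-level bootstrap that refits the model in each resample and keeps all copies of a patient in one fold. Do not bootstrap fixed out-of-fold scores, which under-cover.
- If an untouched hold-out is preferred, keep the split, fix its seed in advance, state that selection uses the training half only, and compute the reader AUC on the same 30 test lesions. This aligns the comparison but does not recover the precision.

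Cost: SAP wording and analysis code. Under Section 4.6 the five readers already evaluate all study imaging, so no patients, images or reads are added. Downsides: no untouched hold-out remains, the cross-validated AUC is pessimistic by about 0.01 to 0.03 for the 60-lesion model, and the refit-bootstrap interval is conservative. The gain is a better model and a more precise, reproducible estimate.

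### The malignancy model has no safeguard against too many tortuosity metrics for about 15 malignant training images: its only reduction step is triggered by pairwise correlation and relies on linear discriminant analysis with no selection rule

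*Combined protocol and SAP*

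**What the plan says.** Under Image Segmentation and Tortuosity Quantification (10.2.2), "a series of tortuosity metrics will be calculated" for the vessels in each lesion. That there is more than one metric is clear from the metric-by-metric t-tests, "incorporating a Bonferroni correction to account for multiple hypothesis testing". The metrics are neither listed nor counted.

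Under Predicting Malignancy (10.2.2), "the set of images will be randomly divided into two halves to form a training data set and a test data set", with malignant and benign lesions allocated separately. The model is named only by type: "Multivariate binary logistic regression will be used to predict malignancy". No penalty, cap on the number of metrics or pre-specified subset is mentioned; the fit is simply "based on the full set of tortuosity metrics for the training data set of 30 images".

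The check and its remedy follow. "We will examine the model for multicollinearity using pairwise correlations", with no threshold given. The analysts will then "perform linear discriminant analysis to choose a smaller subset of metrics if over-fitting due to multicollinearity appears to be a problem", with no selection rule and no criterion for when a problem appears to exist. The fitted model is applied to the other 30 images, and its ROC area is compared with that of the readers.

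**The concern.** Two different problems are treated as one. Collinearity makes individual coefficients unstable. Over-fitting comes from estimating too many coefficients for the number of events, and it happens just as readily when the metrics are uncorrelated. A check based on pairwise correlation looks for the first and can miss the second.

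The remedy does not match the task either. Ordinary linear discriminant analysis gives a weight to every metric and uses the same covariance matrix that collinearity makes ill-conditioned. Some added rule would have to do the selecting, and none is named.

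Objective 2.2.3 is to build this score and objective 2.2.4 is to compare it with the readers. If the fit wastes information, tortuosity will look less useful than it is, for a reason that has nothing to do with tortuosity. If the two classes separate completely in training, the maximum-likelihood coefficients do not exist and the plan gives no fallback.

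**Working it through.** **1. Training size.** Section 10.1 states: "With 60 lesions and 5 readers, where we anticipate that roughly half will be malignant". The split gives 60 / 2 = 30 training images, which agrees with the plan, and about 30 / 2 = 15 malignant and 15 benign. The plan gives no sample-size or performance figure for the model itself; the power calculation in 10.1 concerns reader specificity only.

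**2. Events per metric.** This is 15 / p. The value of p is an assumption, taken over 2 to 15: 7.5 (p = 2), 5 (p = 3), 3 (p = 5), 1.5 (p = 10), 1 (p = 15).

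**3. Size of the over-fitting.** Simulation, 600 replicates per setting: normal uncorrelated metrics, two of them informative, unpenalised logistic fit to 15 + 15 images, tested on 15 + 15 new images. Best achievable AUC is set at 0.80. Loss = 0.80 minus mean test AUC.

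| p | Training AUC | Test AUC | Loss | Complete separation |
|---|---|---|---|---|
| 2 | 0.820 | 0.791 | 0.009 | 0.0% |
| 3 | 0.834 | 0.767 | 0.033 | 0.7% |
| 5 | 0.860 | 0.744 | 0.056 | 2.5% |
| 7 | 0.887 | 0.704 | 0.096 | 7.3% |
| 10 | 0.936 | 0.685 | 0.115 | 31.8% |
| 15 | 0.985 | 0.638 | 0.162 | 83.3% |

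With a best achievable AUC of 0.76 and uncorrelated metrics, p = 8 gives training 0.88 against true 0.66 to 0.67 (loss 0.76 - 0.66 = 0.10). At p = 12, training is 0.94 to 0.95 against true about 0.62 (loss 0.76 - 0.62 = 0.14), with separation in 40 to 51% of samples. With a best achievable AUC of 0.90 and p = 5, the test AUC is still 0.854.

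**4. Would the trigger fire?** The plan sets no threshold; 0.7 and 0.8 are assumed. Across the settings of step 3, repeated with a best AUC of 0.90 and with a common correlation of 0.3, some pair exceeded 0.8 in at most 0.5% of data sets. Over-fitting was marked regardless. With a common correlation of 0.6 the check could well fire: some pair exceeded 0.7 in 91% (p = 5), 97% (p = 8) and 99% (p = 12) of training sets, and exceeded 0.8 in 31%, 48% and 73%.

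**5. Would discriminant analysis or a penalty help?** Best achievable AUC 0.76, common correlation 0.6, all metrics equally informative, 300 replicates, large test sets, ridge penalty tuned inside training. True AUC:

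| p | Maximum likelihood | LDA on all metrics | Ridge | Ridge gain |
|---|---|---|---|---|
| 3 | 0.73 | 0.73 | 0.75 | 0.02 |
| 5 | 0.70 | 0.70 | 0.75 | 0.05 |
| 8 | 0.66 | 0.67 | 0.75 | 0.09 |
| 12 | 0.63 | 0.64 | 0.74 | 0.11 |

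Discriminant analysis does no better than maximum likelihood, to within 0.01. Ridge does much better here, but this pattern favours it: the best score is the plain average of the metrics, which is what ridge shrinks towards. With the same correlation and the signal in one metric only, maximum likelihood against ridge is 0.72 v 0.70 (p = 3), 0.69 v 0.67 (p = 5), 0.66 v 0.64 (p = 8) and 0.62 v 0.62 (p = 12). With uncorrelated metrics, ridge gains 0.01 to 0.04 for p = 3 to 12.

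**6. Precision of the test AUC.** Hanley-McNeil, n = 15 per class, A = 0.80: U = A/(2 - A) = 0.667, V = 2A²/(1 + A) = 0.711. SE² = [A(1 - A) + (n - 1)(U - A²) + (n - 1)(V - A²)]/n² = (0.160 + 0.373 + 0.996)/225 = 0.0068, so SE = 0.082 and the 95% half-width is about 0.16.

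**The case against.** **The held-out half protects the result.** This stands as far as it goes. The AUC compared with the readers comes from lesions not used in fitting, so a reader who inferred that the reported AUC is inflated would be wrong. Holding lesions out does not make the fitted score any better, though.

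**The documents do not show that the score will lose to the readers.** Correct. A reader might infer that it will under-perform, but p, the metrics' true discrimination and the readers' AUC are all unstated. At p = 2 the loss is about 0.01, small against a half-width of about 0.16.

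**Nothing says the test half is used for model building.** Also correct. A reader might infer leakage, on the argument that over-fitting shows only when training and test performance are compared. Large standard errors, separation or cross-validation inside training would reveal it too, and the plan describes the check before the model is applied to the test images. What remains is that the criterion is unstated and use of the test half is not ruled out.

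**Discriminant analysis may mean a stepwise version or a ranking by loadings.** Possible. The defect is then an unnamed rule, and a stepwise search with 15 lesions per class is itself unstable.

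**Ridge is a preference, not a correction.** Partly fair. Its large gains depend on correlated metrics with similar signal, and it can lose slightly otherwise. Limiting the metrics in advance may matter more: in step 3 the test AUC is 0.79 at p = 2 against 0.69 at p = 10. A fixed small subset is therefore an equal alternative.

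**Conclusion.** The point holds. A logistic model on an unstated number of metrics, with about 15 malignant training images, has no safeguard against over-fitting from the number of metrics. The planned check can stay silent while over-fitting is marked, and discriminant analysis on all metrics does not repair the fit.

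The consequence is a score that tends to understate what tortuosity can achieve, and unstable or non-existent coefficients under separation. At a best achievable AUC of 0.76 to 0.80, the loss is roughly 0.01 to 0.05 for p = 2 or 3, about 0.10 at p = 8 and about 0.14 at p = 12, with complete separation in roughly 40 to 50% of samples at p = 12.

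These sizes rest on assumed values: p, normally distributed metrics, the best achievable AUC and where the signal sits. They show direction and range and do not predict this trial's result. The reading that no penalty is intended rests on the plan's silence. The objectives affected are secondary, so this is a worthwhile low-cost improvement and no threat to the primary analysis.

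**What to change.** In 10.2.2, Predicting Malignancy:

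- List the tortuosity metrics and state their number.
- Replace the correlation trigger and the discriminant-analysis step with one of two options: (a) penalised logistic regression, for example ridge, on standardised metrics, with the penalty chosen by cross-validation inside the training half only; or (b) a small subset of metrics fixed before anyone links the metrics to pathology.
- State that no modelling decision uses test lesions. Under option (b) this also means not choosing metrics from the metric-by-metric t-tests, which as written are not confined to the training half.

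The cost is a few lines of text and standard software, with no new data. The expected gain in true AUC from ridge is usually 0.00 to 0.07. It could reach about 0.14 (the whole loss at p = 12) if all metrics are correlated and carry similar signal; the largest gain in the tabulated runs is 0.11. The downsides are that shrunken coefficients are not read as odds ratios, which these objectives do not need, and that ridge can lose up to about 0.02 AUC if only one or two of several correlated metrics carry the signal.
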